9.5.6.1 Urine Pregnancy Test – if applicable

Urine pregnancy test will be performed at the site on female participants of childbearing potential as specified in the SoA (Section 2). A positive urine pregnancy test should be followed up with a serum pregnancy test performed by the central laboratory. Collection, storage, and shipment of serum for pregnancy testing should be performed as described in the Central Laboratory Manual.

9.6 Pharmacokinetics

The decision as to which plasma samples collected will be assayed for evaluation of PK will be collaboratively determined by the Department of Quantitative Pharmacology and Pharmacometrics (QP2) for assay in an exploratory manner for metabolites and/or additional PK markers.

9.6.1 Blood Collection for Plasma MK-7264

PK samples will be collected at the time points specified in [Table 4](#) and in the SoA (Section 2). Blood collection, storage, and shipment instructions for plasma samples are provided in the Central Laboratory Manual.

Table 4 Pharmacokinetic Samples Collection

Period	Trial Day	PK Sample	Time of Collection of PK Sample
Treatment Period (Stages 1 and 2)	1	X	Predose, 1, 2, 4, 8, and 12 hours postmorning dose
	2	X	Premorning dose
	3		NA
	4	X	Premorning dose
	5		NA
	6		NA
	7	X	Premorning dose, 1, 2, 4, 8, and 12 hours postmorning dose
Abbreviations: NA = not applicable; PK = pharmacokinetic			

A variance in procedure collection times as specified in [Table 5](#) will be permitted.

Table 5 Pharmacokinetic (Blood) Collection Windows

PK Collection Time	PK Collection Window
Pre-dose	Within 15 minutes before dose
1 hr post-dose	± 5 minutes
2 hrs post-dose	± 10 minutes
4 hrs post-dose	± 10 minutes
8 hrs post-dose	± 15 minutes
12 hrs post-dose	± 15 minutes
Abbreviations: PK = pharmacokinetic	

9.7 Pharmacodynamics

Pharmacodynamic parameters will not be evaluated in this study.

9.8 Biomarkers

Collection of samples for other biomarker research is also part of this study. The following samples for biomarker research are required and will be collected from all participants in this study as specified in the SoA (Section 2):

- Blood for genetic analysis

9.8.1 Planned Genetic Analysis Sample Collection

The Planned Genetic Analysis sample should be drawn for planned analysis of the association between genetic variants in DNA and drug response. This sample will not be collected at the site if there is either a local law or regulation prohibiting collection, or if the IRB/IEC does not approve the collection of the sample for these purposes. If the sample is collected, leftover extracted DNA will be stored for future biomedical research if the participant signs the Future Biomedical Research consent. If the planned genetic analysis is not approved, but Future Biomedical Research is approved and consent is given, this sample will be collected for the purpose of Future Biomedical Research.

Sample collection, storage and shipment instructions for Planned Genetic Analysis samples will be provided in the Central Laboratory Manual.

9.9 Future Biomedical Research Sample Collection

If the participant signs the Future Biomedical Research consent, the following specimens will be obtained as part of Future Biomedical Research:

- DNA for future research

9.10 Visit Requirements

Visit requirements are outlined in Section 2 – Schedule of Activities (SoA). Specific procedure-related details are provided above in Section 9 – Study Assessments and Procedures.

All study procedures will be performed as specified in the SoA (Section 2).

The PROs (CSD, Cough Severity VAS, LCQ-acute, and WURSS-24) should be performed in the same order each evening, as listed in the SoA (Section 2.0).

Additional details of certain procedures at specific visits are described in this section.

9.10.1 Screening Period

9.10.1.1 Visit 1

During the Screening Period, between Days -28 to -3, potential participants will be evaluated to determine their eligibility as described in Sections 6.1 and 6.2. Screening procedures may be repeated after consultation with the Sponsor.

Participants may be rescreened once within 30 days of not meeting entry criteria during the screening period. Rescreening should include all screening procedures listed in the SoA (Section 2), including consent review. A consultation or Sponsor Consultation Form is not required for rescreening a participant. Note: Participants who were previously randomized and discontinued due to lack of viral shedding within 72 hours of inoculation (or discontinued for any other reason) may not be rescreened for this trial.

9.10.1.2 Visit 2 (Day -2)

Eligible participants will be admitted to the clinic on Day -2 and will remain confined to the clinic until completion of the treatment period on Day 7 and discharged on Day 8 (or until discontinuation).

9.10.1.3 Visit 3 (Day -1; Baseline Visit)

Study clinic staff will instruct participants on how to properly complete study-related questionnaires (ie, Cough Severity VAS, CSD, LCQ-acute, and WURSS-24) and evaluate participant's capability to understand and complete the questionnaires for the duration of the trial. Note: Study clinic staff must never implement any updates on behalf of the participant or provide any interpretation of the questions.

On Day -1 of Stage 1, the ATP cough challenge will be administered to participants as described in Section 9.2.3. The number of coughs will be monitored manually at this visit. Details of the cough challenge procedures are provided in the Procedures Manual.

Note: ATP cough challenge is NOT performed during Stage 2 of the trial.

9.10.2 Treatment Period (Days 1 through 7)

Beginning at the randomization visit (Day 1), the cough monitor will be attached to the participant as described in Section 9.2.1. On Days 1 through 7, the CF card and battery pack must be removed from the cough monitor and replaced with a new CF card and new battery pack every 24 hours. Each CF card will then be sent for analysis, as described in the VitaloJAK™ Manual.

Note: The cough monitor can be removed for approximately 15 minutes each day, prior to taking a shower, with the assistance of site staff.

During Stage 1 of the trial, ATP cough challenge will be performed on all randomized participants 2 hours (\pm 30 minutes) postmorning dose as per the SoA (Section 2). The ATP cough challenge will NOT be performed during Stage 2 of the trial.

At the Discharge Visit (Day 8), a limited physical exam may be performed instead of a full physical exam, based on investigator judgment. Women of child bearing potential should be reminded to continue use of appropriate contraception (see Appendix 3) for at least 14 days after the last dose of study treatment.

9.10.3 Discontinued Participants Continuing to be Monitored in the Study

If a participant is discontinued from the study treatment, discontinuation procedures should be performed as specified in the SoA (Section 2). The participant will then be discharged from the study clinic and will be informed that they will receive a post-study telephone follow-up approximately 14 days (+ 3 days) after the last dose of study treatment.

Details about discontinuation of participants who do not show confirmation of HRV-16 shedding by nasal swab testing within 72 hours of inoculation are described in Section 9.1.11.

9.10.4 Post-study Telephone Follow-Up

Participants will be contacted for a safety follow-up phone call approximately 14 days (+ 3 days) after the last dose of study treatment. If the post-study telephone contact visit occurs less than 14 days after the last dose of study treatment, a subsequent follow-up phone call should be made at 14 days after the last dose of study treatment to determine if any AEs have occurred since the post-study telephone contact visit.

No other safety or efficacy assessments are required after discharge from the clinic; however, additional safety follow up may be performed, at the discretion of the investigator.

WOCBP potential must continue to use an acceptable birth control (defined in Appendix 3) for at least 14 days after the last dose of study treatment.

10. Statistical Analysis Plan

This section outlines the statistical analysis strategy and procedures for the study. Changes to analyses made after the protocol has been finalized, but prior to unblinding, will be documented in a supplemental Statistical Analysis Plan (sSAP) and referenced in the Clinical Study Report (CSR) for the study. Post hoc exploratory analyses will be clearly identified in the CSR.

10.1 Statistical Analysis Plan Summary

Key elements of the Statistical Analysis Plan (SAP) are summarized below. The comprehensive plan is provided in Sections 10.2 to 10.12.

Study Design Overview	A Phase 2a, double-blind, randomized, placebo-controlled, parallel-group trial to study efficacy, safety, and tolerability in male and female healthy participants with induced viral URTI.
Treatment Assignment	
In Stage 1 (prior to the IA), participants will be randomized in a 1:1 randomization ratio to MK-7264 45 mg BID or placebo.
 
In Stage 2 (post-IA), if a decision is made to include a lower dose of MK-7264 based on the IA results, participants will be randomized to MK-7264 45 mg BID, MK-7264 15 mg BID, or placebo in a 1:2:1 ratio, respectively. Otherwise, the 1:1 randomization ratio to MK-7264 45 mg BID or placebo will be used in Stage 2.
 
Randomization will be stratified by gender and site.

Analysis Populations
	
Efficacy: The modified Full Analysis Set (mFAS) population, which consists of all randomized participants who receive at least one dose of study treatment and have confirmation of viral shedding within 72 hours of administration of HRV-16; and Per Protocol (PP) Population, which excludes participants due to major deviations from the protocol from the mFAS population.
 
Safety: All Participants as Treated (APaT) population, which consists of all randomized participants who received at least one dose of study treatment.
 
PK: Population that includes all participants with at least one measurable PK sample.

Primary Endpoint
	
Awake coughs per hour on Day 3 of treatment.

Key Secondary Endpoints
	
 • Cough Severity VAS score measured as change from baseline on Day 3 • CSD score measured as change from baseline on Day 3 • LCQ-acute score measured as change from baseline on Day 3

Statistical Methods for Key Efficacy Analyses
	
The primary efficacy endpoint will be analyzed using a longitudinal data analysis model (LDA). In this model, the response vector consists of daily awake coughs per hour at each postbaseline visit. Covariates will include treatment, visit, the interaction of treatment by visit, gender, and site. The unstructured approach will be used to model the covariance of the repeated cough measurements over time within participants. Additional covariance structures, such as Toeplitz covariance, may be considered if convergence issues are encountered with the analysis model.

Statistical Methods for Key Safety Analyses
	
The analysis of safety endpoints will follow a tiered approach. The tiers differ with respect to the analyses that will be performed. Tier 1 safety endpoints will be subject to inferential testing for statistical significance with p-values and 95% confidence intervals (CIs) provided for between-group comparisons. Tier 2 safety endpoints will be evaluated via point estimates and 95% CIs for between-group comparisons. Tier 3 safety endpoints will be evaluated via point estimates only.

Interim Analyses
	
One planned efficacy IA will be performed in this study. Results will be reviewed by an internal data monitoring committee (ie, siDMC). This IA is summarized below.
 
 • Timing: To be performed when approximately 50 participants have completed (or discontinued early from) Stage 1 of the trial • Purposes: 
 ○ Conduct a futility analysis ○ Re-estimate sample size ○ Potentially add a lower dose (15 mg BID) of MK-7264 if a certain magnitude of efficacy of MK-7264 45 mg BID is detected compared with placebo ○ Evaluate safety and tolerability of MK-7264 
Details are described in Section 10.7.1.

Multiplicity
	
No multiplicity adjustment is planned as there are no hypotheses for this study.

Sample Size and Power
	
The planned sample size is 100 participants, up to a maximum of 188 participants.
 

10.2 Responsibility for Analyses/In-house Blinding

The statistical analysis of the data obtained from this study will be the responsibility of the designee of the Sponsor.

The study will be conducted as a double-blind study under in-house blinding procedures. The official, final database will not be unblinded until medical/scientific review has been performed, protocol violators have been identified, and data have been declared final and complete.

Treatment assignment will be implemented by the external vendor of the study IVRS according to the adaptive allocation scheme provided in Section 7.3.

Unblinding for Efficacy and Safety Interim Analyses

Treatment-level results and/or participant-level data of the IA will be provided by an internal unblinded statistician to the siDMC.

The interim efficacy and safety analyses will be conducted by the unblinded statistician; the results will be reviewed and decision made by a siDMC that consists of Sponsor personnel. Limited additional Sponsor personnel may be unblinded to the treatment-level results of the IA, if required, in order to act on the recommendations of the siDMC. The details of the

siDMC monitoring guidelines, scope of work, the schedule of the interim safety monitoring, and stopping rules will be described in the Protocol-specific siDMC Charter. The extent to which individuals are unblinded with respect to results of IAs will be documented by the unblinded statistician. These individuals will not be involved in the day-to-day operations of the study.

The processes by which recommendations and decisions are reached and communicated are documented in the siDMC charter for the Sponsor. The protocol-specific siDMC charter will be referenced in the CSR. Prior to final study unblinding, individuals who have been unblinded at any level will not be involved in any discussions regarding modifications to the protocol, statistical methods, identification of protocol deviations, or data validation efforts after the interim analyses.

10.3 Hypotheses/Estimation

There are no hypotheses for this study.

10.4 Analysis Endpoints

Efficacy and safety endpoints that will be evaluated for within- and between-treatment differences are listed below, followed by the descriptions of the derivations of selected endpoints.

10.4.1 Efficacy Endpoints

Primary Efficacy Endpoint

Awake cough frequency (coughs per hour) on Day 3, as assessed by an objective cough-counting device

Secondary Efficacy Endpoints

- Cough Severity VAS score measured as change from baseline on Day 3
- CSD score measured as change from baseline on Day 3
- LCQ-acute score measured as change from baseline on Day 3

Exploratory Efficacy Endpoints

Exploratory efficacy endpoints are stated in Section 4.

10.4.2 Safety Endpoints

Safety endpoints are stated in Section 4.

10.4.3 Pharmacokinetic Endpoints

PK endpoints are stated in Section 4.

10.4.4 Derivations of Efficacy Endpoints

The primary efficacy endpoint of this study is the awake coughs per hour on Day 3 of the treatment period. It is calculated as:

Awake coughs per hour = Total number of cough events during the monitoring period (24-hour interval) the participant is awake / Total duration (in hours) for the monitoring period the participant is awake

Awake is time between waking up and sleep during the 24-hour monitoring period.

10.5 Analysis Populations

10.5.1 Efficacy Analysis Populations

The modified Full Analysis Set (mFAS) population will serve as the primary population for the analysis of efficacy data in this study. The mFAS population consists of all randomized participants who receive at least one dose of study treatment and have confirmation of viral shedding within 72 hours of administration of HRV-16.

The Per Protocol (PP) population excludes participants due to major deviations from the protocol that may substantially affect the results of the primary efficacy endpoint. Potential deviations that may result in the exclusion of a participant from the PP population will be specified in the sSAP. The final determination on major protocol deviations, and thereby the composition of the PP population, will be made prior to the final unblinding of the database and will be documented in a separate memo. A supportive analysis using the PP population may be performed for the primary efficacy endpoint if the proportion of the participants with major protocol deviations is >10%.

Participants will be included in the treatment group to which they are randomized for the analysis of efficacy data using both the mFAS and PP populations. Details on the approach to handling missing data are provided in Section 10.6.

10.5.2 Safety Analysis Populations

The All Participants as Treated (APaT) population will be used for the analysis of safety data in this study. The APaT population consists of all randomized participants who received at least one dose of study treatment. Participants will be included in the treatment group corresponding to the study treatment they actually received for the analysis of safety data using the APaT population.

At least one laboratory or vital sign measurement obtained subsequent to at least one dose of study treatment is required for inclusion in the analysis of each specific parameter. To assess change from baseline, a baseline measurement is also required.

Details on the approach to handling missing data for safety analyses are provided in Section 10.6.

10.5.3 Pharmacokinetic Analysis Population

The evaluable PK population for PK data analysis is defined as all participants with at least one measurable PK sample.

10.6 Statistical Methods

Statistical testing and inference for efficacy and safety analyses are described in Section 10.6.1 and Section 10.6.2, respectively.

10.6.1 Statistical Methods for Efficacy/Immunologic Analyses

Primary Efficacy Analysis

The primary analysis will be conducted on the mFAS population.

The primary efficacy endpoint for the study is the awake coughs per hour on Day 3 of treatment. It will be analyzed using a longitudinal data analysis (LDA) model. In this model, the response vector consists of daily awake coughs per hour at each post-baseline visit; and covariates will include treatment, visit, the interaction of treatment by visit, gender, and site. The unstructured approach will be used to model the covariance of the repeated cough measurements over time within participants. Additional covariance structures, such as Toeplitz covariance, may be considered if convergence issues are encountered with the analysis model.

Point estimates and two-sided 95% confidence interval (CI) of the treatment difference in adjusted means will be presented.

Secondary Efficacy Analysis

The secondary efficacy endpoints will be analyzed based on the mFAS population using a longitudinal analysis of covariance (ANCOVA) model. In this model, the response vector consists of the change from baseline value at each post-baseline visit. The model will adjust for treatment, visit, the interaction of treatment by visit, gender, site, and baseline value as a covariate. Further details of the model specification, assumptions, and SAS implementation codes will be provided in the sSAP. [Table 6](#) summarizes the key analyses.

Table 6 Analysis Strategy for Key Efficacy Endpoints

Endpoint	Statistical Method	Missing Data Approach
Primary Efficacy Endpoint		
Awake coughs per hour on Day 3	LDA	Model-based
Secondary Efficacy Endpoints		
Change from Baseline in daily Cough Severity VAS on Day 3	Longitudinal ANCOVA	Model-based
Change from Baseline in daily CSD on Day 3	Longitudinal ANCOVA	
Change from Baseline in daily LCQ-acute total score on Day 3	Longitudinal ANCOVA	
Abbreviations: LDA = longitudinal data analysis; ANCOVA = analysis of covariance; VAS = Visual Analogue Scale; CSD = Cough Severity Diary; LCQ = Leicester Cough Questionnaire; mFAS = modified Full Analysis Set		
Note: Efficacy analysis will be based on the mFAS.		

Exploratory Efficacy Analysis

Details of the exploratory efficacy analysis methods will be provided in the sSAP.

Handling of Missing Data

No missing data will be imputed. All analyses will be conducted based on the observed data only.

10.6.2 Statistical Methods for Safety Analyses

Safety and tolerability will be assessed by clinical review of all relevant parameters including AEs, laboratory tests, vital signs, and ECG measurements.

The analysis of safety results will follow a tiered approach (Table 7). The tiers differ with respect to the analyses that will be performed. Tier 1 safety endpoints will be subject to inferential testing for statistical significance with p-values and 95% CIs provided for between-group comparisons. Tier 2 safety endpoints will be evaluated via point estimates and 95% CIs for between-group comparisons. Tier 3 safety endpoints will be evaluated via point estimates only.

Adverse experiences (specific terms as well as system organ class terms) and predefined limits of change in laboratory, vital sign, and ECG parameters will be classified as belonging to "Tier 2" or "Tier 3", based on the number of events observed. Membership in Tier 2 requires that at least 4 participants in any treatment group exhibit the event; all other AEs and predefined limits of change will belong to Tier 3.

The threshold of at least 4 events was chosen because the 95% CI for the between-group difference in percent incidence will always include zero when treatment groups of equal size each have less than 4 events and thus, would add little to the interpretation of potentially meaningful differences. Because many 95% CIs may be provided without adjustment for multiplicity, the CIs should be regarded as a helpful descriptive measure to be used in review, not a formal method for assessing the statistical significance of the between-group differences in AEs and predefined limits of change.

Continuous measures such as changes from baseline in laboratory, vital sign, and ECG parameters will be considered Tier 3 safety parameters. Summary statistics for Baseline, on-treatment, and change from Baseline values will be provided by treatment group in table format.

For this protocol, a composite endpoint of taste-related AEs (including dysgeusia, ageusia, and hypogeusia, as well as other related terms) is considered a Tier 1 event. In addition, the broad clinical and laboratory AE categories consisting of the percentage of participants with any AE, a drug-related AE, an SAE, an AE which is both drug-related and serious, any oral paresthesia AE, any oral hypoesthesia AE, and discontinuations due to an AE will be considered Tier 2 endpoints. P-values (Tier 1 only) and 95% confidence intervals (Tier 1 and Tier 2) will be provided for between-treatment differences in the percentage of participants with events; these analyses will be performed using the Miettinen and Nurminen method (1985), an unconditional, asymptotic method [Miettinen, O. and Nurminen, M. 1985].

Table 7 Analysis Strategy for Safety Parameters

Safety Tier	Safety Endpoint [†]	p-Value	95% CI for Treatment Comparison	Descriptive Statistics
Tier 1	Any taste-related AE	X	X	X
Tier 2	Any oral paresthesia AE		X	X
	Any oral hypoesthesia AE		X	X
	Any AE		X	X
	Any SAE		X	X
	Any drug-related AE		X	X
	Any serious and drug-related AE		X	X
	Discontinuation due to AE		X	X
	Specific AEs, SOCs, or PDLCs [‡] (incidence ≥4 participants in one of the treatment groups)		X X	X X
Tier 3	Specific AEs, SOCs or PDLCs [‡] (incidence <4 participants in all of the treatment groups)			X
	Change from Baseline Results (Labs, ECGs, Vital Signs)			X
Abbreviations: AE = adverse event; CI = confidence interval; ECG = electrocardiogram; PDLC = pre-defined limit of change; SAE = serious adverse event; SOC = system organ class; X = results will be provided [†] Adverse Experience references refer to both Clinical and Laboratory AEs. [‡] Includes only those endpoints not pre-specified as Tier 1 or not already pre-specified as Tier-2 endpoints.				

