7.3.1 Stratification

Treatment allocation/randomization will be stratified according to the following factors:

- Gender (Male, Female)
- Site

The IVRS/IWRS will stratify participants by gender and at a site level. The study will endeavor to enroll a minimum of ~ 40% female participants in each stage. At the site level, the IVRS/IWRS will randomize participants to ensure there is a balance among treatment groups.

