10.8 Multiplicity

There are no hypotheses for this study. For Tier 1 safety endpoints, 95% CIs for between-group differences will be provided with nominal p-values as a descriptive measure without adjustment for multiplicity. There will be no formal method for assessing statistical significance.

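### The Tier 1 taste comparison and the Tier 2 safety intervals name no strata although randomisation is stratified by gender and site: mildly conservative for 45 mg versus placebo, and open to shifts in mix between stages for any 15 mg contrast.

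*Combined protocol and SAP*

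**What the plan says.** Section 7.3.1: "Treatment allocation/randomization will be stratified according to the following factors", and the factors listed are gender and site. The only stated control on gender mix by stage is a soft floor: "The study will endeavor to enroll a minimum of ~ 40% female participants in each stage". No site quota is given.

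Section 10.6.1, primary model: "covariates will include treatment, visit, the interaction of treatment by visit, gender, and site". The secondary models also adjust for gender and site.

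Section 10.6.2, safety: "P-values (Tier 1 only) and 95% confidence intervals (Tier 1 and Tier 2) will be provided" for differences in the percentage of participants with events, and "these analyses will be performed using the Miettinen and Nurminen method (1985), an unconditional, asymptotic method". No strata, weights or covariates are named. Any taste-related AE is the only Tier 1 endpoint (Table 7), so it carries the only p-value that the plan specifies.

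The plan describes that p-value in two ways. Section 10.6.2 states "Tier 1 safety endpoints will be subject to inferential testing for statistical significance with p-values and 95% CIs provided for between-group comparisons". Section 10.8 states "95% CIs for between-group differences will be provided with nominal p-values as a descriptive measure without adjustment for multiplicity".

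Sections 5.1, 7.3 and 10.9: Stage 1 has about 25 participants each on 45 mg and placebo. If 15 mg is added, Stage 2 randomises 1:2:1 (45 mg : 15 mg : placebo), to reach about 50 per group and 150 in total.

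**The concern.** A trial randomised within gender and site is analysed for safety as if it were not. When a stratification factor predicts the outcome, the unstratified variance includes between-stratum variation that the randomisation has already balanced out, so the standard error is too large. Taste events are reported by participants and elicited by site staff (Sections 9.3.2 and 9.5.5), so differences in reporting between sites are plausible.

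The second issue arises only in the three-arm design. All 15 mg participants would come from Stage 2, while half of the 45 mg and placebo participants would come from Stage 1. Stratified randomisation cannot balance gender and site between arms recruited in different stages. The efficacy models would adjust for such a shift, but the crude safety contrasts would not.

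Section 5.5.1 treats both efficacy and dysgeusia as dose-related and gives the balance between them as the reason for studying two doses. The taste contrast between 45 mg and 15 mg bears directly on that purpose.

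**Working it through.** **1. The plan's own figures.** Stage 1 is 25/25. Stage 2 is 100 at 1:2:1, or 25/50/25. The totals are 25+25 = 50 on 45 mg, 50 on 15 mg and 25+25 = 50 on placebo, so 150, as in Table 10. The 50 per group is reached only by pooling Stage 1.

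Section 10.6.2 sets the Tier 2 threshold at 4 events. The Miettinen-Nurminen statistic at zero difference is z = d / √[p(1−p)(1/n₁+1/n₂)·N/(N−1)].
- 3 versus 0 of 50: 0.06/√(0.03×0.97×0.04×100/99) = 1.75, p = 0.080.
- 4 versus 0 of 50: 0.08/√(0.04×0.96×0.04×100/99) = 2.03, p = 0.042.

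The stated threshold reproduces.

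**2. 45 mg versus placebo.** Simulation of 200,000 trials per scenario with no treatment effect, 50 per arm, and four gender-by-site strata of 15/15/10/10 in each arm. The stratified test uses weights n₁n₂/N. The stratum differences in taste reporting are assumptions.

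| Assumed stratum difference | True SD (points) | Mean unstratified SE | Ratio | Rejection, unstratified | Rejection, stratified |
|---|---|---|---|---|---|
| none | 8.02 | 7.98 | 1.00 | 0.050 | 0.051 |
| gender 10 | 7.79 | 7.82 | 1.00 | 0.048 | 0.051 |
| gender 20 | 7.43 | 7.66 | 1.03 | 0.041 | 0.050 |
| gender 20 + site 20 | 8.53 | 8.97 | 1.05 | 0.040 | 0.050 |
| gender 40 | 7.86 | 8.77 | 1.12 | 0.030 | 0.050 |
| gender 40 + site 20 | 8.14 | 9.25 | 1.14 | 0.025 | 0.049 |

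The mean difference is zero throughout, because this contrast is 1:1 in both stages. With a true difference of about 20 points, stratifying raised power by 0 to 2 points (0.829 to 0.845 with a gender difference; 0.834 to 0.854 with gender and site differences).

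**3. 15 mg contrasts: formula.** Half of the pooled comparator arm comes from Stage 1 and none of the 15 mg arm does. Relative to the Stage 2 mix, the distortion is therefore ½ × (shift in mix) × (rate gap between strata in the comparator arm).
- Female share 40% then 60%, 20-point gap: ½ × 0.20 × 20 = 2.0 points; simulated rejection with no effect 0.049.
- Site mix 80/20 then 20/80, 20-point gap: ½ × 0.60 × 20 = 6.0 points; rejection 0.10.

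Stratifying by the shifting factor returned the mean difference to zero (within 0.1 point) and rejection to about 0.05.

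**4. 15 mg contrasts: example with dose effects.** Assume 40% female in Stage 1 and 60% in Stage 2, with taste rates for men/women of 40/70% on 45 mg, 15/35% on 15 mg and 5/10% on placebo. Then 45 mg and placebo each have 25 men and 25 women, and 15 mg has 20 men and 30 women.
- Crude rates: 45 mg 55%; 15 mg (20×0.15+30×0.35)/50 = 27%; placebo 7.5%.
- Weights: men 25×20/45 = 11.11, women 25×30/55 = 13.64, or 0.449 and 0.551.
- 45 mg minus 15 mg: crude 28.0; stratified 0.449×25+0.551×35 = 30.5.
- 15 mg minus placebo: crude 19.5; stratified 0.449×10+0.551×25 = 18.3.

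Crude and stratified estimates differ by 2.5 and 1.2 points.

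**5. What gender and site strata do not remove.** An assumed 10-point stage effect not carried by either factor leaves −5.0 points of bias in 15 mg versus placebo, with or without stratification (rejection 0.09 both ways).

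**The case against.** The strongest reply is that little rests on these numbers. Section 10.3 states no hypotheses, Section 10.8 calls the p-values nominal and descriptive, and no decision rule in the visible text uses them. Table rows with material over-width need large assumed differences, and nothing in the documents says that gender or site predicts taste events. All of this stands and sets the weight of the point. Conservatism is not wholly harmless in a tolerability comparison, however, because it slightly reduces the chance of showing a real excess.

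A reader might infer that the unstratified p-value is invalid or too liberal. For 45 mg versus placebo the documents do not support that: allocation is 1:1 in both stages, so the estimate is unbiased and the error rate falls at or below nominal.

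A second reply concerns the example. Its risk differences vary by gender, so the weights also change what is estimated. In the Stage 2 mix, the true 15 mg minus placebo difference is 0.4×10+0.6×25 = 19.0, and the crude 19.5 is closer than the stratified 18.3. That is correct. For 45 mg minus 15 mg the order reverses: the truth is 0.4×25+0.6×35 = 31.0, against 28.0 crude and 30.5 stratified. In a 50/50 mix the truths are 17.5 and 30.0, and stratified is closer for both. Either way the shifts are small beside sampling error. The Wald 95% half-widths are 1.96×√(0.55×0.45/50+0.27×0.73/50) = 18.5 points and 1.96×√(0.27×0.73/50+0.075×0.925/50) = 14.3 points.

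Third, the root of the 15 mg issue is non-concurrent comparison, which gender and site strata address only in part. Stages also differ in the ATP challenge (Stage 1 only, Section 9.2.3) and, with three arms, in tablets per dose (Section 9.1.8). This stands, and the fix has to reflect it.

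Finally, Section 10.6.2 does not exclude strata, and the supplemental SAP, which is not among the documents, could add them.

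**Conclusion.** The point holds as a minor improvement to the analysis. The safety method, as written, ignores the factors by which the trial is randomised.

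- **45 mg versus placebo:** no bias. The standard error is about 0% to 14% too large under the assumed differences, with the upper end needing a 40-point gender plus a 20-point site difference. The effect is nil if neither factor predicts taste reporting.
- **15 mg contrasts:** these absorb about half of any gender or site shift between stages, about 1 to 3 points in the gender example and about 6 in the site reversal. This applies only if the arm opens and Stage 1 participants are pooled. The group sizes imply pooling, but the safety section does not state it.

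A reader might also infer that stratifying by gender and site makes the 15 mg contrasts safe from stage effects. It does not: it removes the shift in those two factors and nothing else.

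**What to change.** In Section 10.6.2, specify the stratified Miettinen-Nurminen method with gender and site as strata and Cochran-Mantel-Haenszel weights for the Tier 1 taste endpoint, and for the pre-specified Tier 2 categories where events are not sparse. State a rule for pooling sites that have an empty arm within a gender. Keep crude incidences for display.

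If the 15 mg arm opens, add a sensitivity analysis of its contrasts using only concurrent Stage 2 participants. By the planned allocation that is about 50 on 15 mg against about 25 in each comparator, so it will be less precise than the pooled contrast.

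The cost is a few sentences and a stratified form of the method already chosen. If gender and site do not matter, the stratified interval is about the same width at 50 per arm (ratio 1.001) and up to about 2% wider at 25 per arm (highest ratio 1.017). Those ratios come from a small simulation of 600 trials per scenario with four strata, so they are approximate.
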